1. LIST OF ABBREVIATIONS

Table 1: List of Abbreviations

ACT	Asthma Control Test
AE	Adverse Event
ATS	American Thoracic Society
AUC	Area under the curve
BID	Twice a day
CASI	Composite Asthma Severity Index
CFR	Code of Federal Regulations
CR	Cockroach
CRF	Case Report Form
CTCAE	Common Terminology Criteria for Adverse Events
DAIT	Division of Allergy, Immunology, and Transplantation
DSMB	Data Safety Monitoring Board
eCRF	Electronic Case Report Form
E&M	Evaluation and Management
FDA	Food and Drug Administration
FENO	Fractional Exhaled Nitric Oxide
FEV ₁	Forced Expiratory Volume in 1 second
GCP	Good Clinical Practice
HIPPA	Health Insurance Portability and Accountability Act
IB	Investigator Brochure
ICAC	Inner-City Asthma Consortium
ICH	International Conference on Harmonization
ICS	Inhaled Corticosteroid
IgE	Immunoglobulin E
IgG	Immunoglobulin G
IND	Investigational New Drug
IRB	Institutional Review Board
ITT	Intent-to-treat
LABA	Long-acting Beta Agonist
MCG	Microgram
MCL	Microliter

National Institute of Allergy and Infectious Diseases
{Statistical Analysis Plan - Protocol #}

MM	Medical Monitor
MOP	Manual of Procedures
NAC	Nasal Allergen Challenge
NAEPP	The National Asthma Education and Prevention Program
NCI	National Cancer Institute
NIAID	National Institute of Allergy and Infectious Diseases
OMB	Office of Management and Budget
PCP	Primary Care Provider
PD	Protocol Deviation
PEF	Peak Expiratory Flow
PFT	Pulmonary Function Tests
PI	[Site] Principal Investigator
SACCC	Statistical and Clinical Coordinating Center
SAE	Serious Adverse Event
SAP	Statistical Analysis Plan
SAR	Suspected Adverse Reaction
SCIT	Subcutaneous Immunotherapy
SLIT	Sublingual Immunotherapy
SOP	Standard Operating Procedure
SUSAR	Suspected Unexpected Serious Adverse Reaction
TLC	Total Lung Capacity
TNSS	Total Nasal Symptom Score
WAO	World Allergy Organization

2. PURPOSE OF THE ANALYSES

The purpose of this statistical analysis plan (SAP) is to describe the planned analyses and data displays to be included in the Clinical Study Report (CSR) for Protocol ICAC-28. This document provides details on study populations, how the variables will be derived, how missing data will be handled and details on statistical methods to be used to analyze the safety and efficacy data.

The statistical analysis plan (SAP) is based on ICH guidelines E3 and E9 (Statistical Principles for Clinical Trials).

The document may evolve over time, for example, to reflect the requirements of protocol amendments or regulatory requests. However, the final SAP must be finalized, approved by the Client, and placed on file before database is locked. If differences occur between analyses described in the SAP and the current protocol, those found in this SAP will assume primacy. Deviations from the final approved plan will be noted in the clinical study report.

3. PROTOCOL SUMMARY

Title	Cockroach Immunotherapy in Children and Adolescents
Short Title	CRITICAL
Clinical Phase	II
Number of Sites	Multiple sites in the United States
IND Sponsor/IND Number	DAIT NIAID, NIH /IND #17979
Study Objectives	
The primary objective of the study is to determine if the NAC response will be changed with treatment with cockroach subcutaneous immunotherapy (SCIT).
 
Secondary objectives are:
 
1. To assess safety of cockroach SCIT in children and adolescents2. To assess the effect of cockroach SCIT on German cockroach-specific IgE and IgG4
Study Design	
This is a 1:1 randomized, double-blind, placebo-controlled, multicenter trial with 2 arms:
 
• Cockroach SCIT• Placebo 
This study will enroll 80 children from 8-17 years of age who are sensitized to cockroach and have asthma and a positive cockroach Nasal Allergen Challenge (NAC) before randomization.

Primary Endpoint(s)	Change in mean TNSS after 12 months of treatment with cockroach SCIT.
Secondary Endpoint(s)	
1. Rate of immunotherapy related adverse events and immunotherapy related serious adverse events in the course of treatment2. Change in additional NAC outcomes from baseline
a. TNSS AUCb. Responsive dose3. Changes in German cockroach-specific IgE and IgG4

National Institute of Allergy and Infectious Diseases
{Statistical Analysis Plan - Protocol #}

Accrual Objective	~80
Study Duration	~48 months
Treatment Description	Non-standardized glycerinated German cockroach (Blattella germanica) allergenic extract or placebo used by subcutaneous administration in escalating doses up to 0.4 ml of 1:10 wt./vol.
Inclusion Criteria	
Individuals who meet all of the following criteria are eligible for enrollment as study participants:
 
1. Subject and/or parent guardian must be able to understand and provide informed consent.2. Are male or female children, 8-17 years of age at recruitment.3. Have a primary place of residence in one of the pre-selected recruitment census tracts as outlined in the Protocol ICAC-28 Manual of Operations (MOP)
a. Participants who do not live in the pre-selected census tracts but live within the Office of Management and Budget (OMB) defined Metropolitan Statistical Area and have publicly-funded health insurance will qualify for inclusion.4. Have a history of persistent asthma for a minimum of 1 year before study entry.
a. A diagnosis of asthma will be defined as a report by the caretaker that the participant had a clinical diagnosis of asthma made by a clinician ≥ 1 year ago, resulting in a prescription of preventative asthma medication.b. The participant must have persistent asthma defined by the current need for at least 88 mcg fluticasone (or the equivalent of another inhaled corticosteroid) to control asthma at the time of screening.5. Before randomization, the participant's asthma must be well-controlled as defined by:
a. A FEV₁ greater than or equal to 80% predicted, andb. An Asthma Control Test (ACT) or Childhood Asthma Control Test (CACT) score ≥ 20.6. Are sensitive to German cockroach as documented by a positive (≥ 3 mm greater than negative control) skin prick test result and detectable German cockroach-specific IgE (≥ 0.35 kU/L).7. Have no known contraindications to therapy with glycerinated German cockroach allergenic extract or placebo.

	
8. Have a positive cockroach Nasal Allergen Challenge (NAC), as defined by reaching a Total Nasal Symptom Score (TNSS) of ≥ 6 or a sneezing score of 3 at dose 2 or above during the challenge before randomization.9. Have documentation of current medical insurance with prescription coverage at randomization.
Exclusion Criteria	
Individuals who meet any of these criteria are not eligible for enrollment as study participants but may be reassessed while enrollment is ongoing. Participants are ineligible if they:
 
1. Are unable or unwilling to give written informed consent or comply with study protocol.2. Are pregnant or lactating. Post-menarcheal females must be abstinent or use a medically acceptable birth control method throughout the study (e.g. oral, subcutaneous, mechanical, or surgical contraception).3. Cannot perform acceptable spirometry or peak flow before randomization.4. Have an asthma severity classification of severe or unstable at the time of randomization, as evidenced by at least one of the following:
a. Require a dose of greater than 500 mcg of fluticasone per day or the equivalent of another inhaled corticosteroid.b. Have received more than 2 courses of oral or parenteral corticosteroids within the 12 months or one course within the last 3 months prior to study entry.c. Have been treated with depot steroids within the 3 months prior to study entry.d. Have been hospitalized for asthma within the 6 months prior to study entry.e. Have had a life-threatening asthma exacerbation that required intubation, mechanical ventilation, or that resulted in a hypoxic seizure within 2 years prior to study entry.5. Do not have access to a phone (needed for scheduling appointments).

	
6. Have received allergen immunotherapy (SLIT or SCIT) in the last 12 months prior to study entry or who plan to initiate or resume allergen immunotherapy during the study.7. Have received biologic therapy (e.g., anti-IgE, anti-IL-4, anti-IL-5) within 6 months of the NAC procedure, if applicable, or Randomization, if no NAC is performed.8. Have received an investigational drug in the 30 days prior to study entry or who plan to use an investigational drug during the study.9. Have past or current medical problems or findings from physical examination or laboratory testing that are not listed above, which, in the opinion of the investigator, may pose additional risks from participation in the study, may interfere with the participant's ability to comply with study requirements or that may impact the quality or interpretation of the data obtained from the study.10. Have nasal polyps or other major structural abnormalities in their nasal cavities as assessed by anterior rhinoscopy. 
Participants who meet any of the following criteria are not eligible for enrollment and may not be reassessed. Participants are ineligible if they:
 
1. Plan to move from the area during the study period2. Have a history of anaphylaxis grade 3 or higher as defined in section 12.3.1.1c, World Allergy Organization Subcutaneous Immunotherapy Systemic Reaction Grading System.3. Have unstable angina, significant arrhythmia, uncontrolled hypertension, history of autoimmune disease, or other chronic or immunological diseases that in the opinion of the investigator might interfere with the evaluation of the investigational product or pose additional risk to the participant.4. Past or current medical problems or findings from physical examination or laboratory testing that are not listed above, which, in the opinion of the investigator, may pose additional risks from participation in the study, may interfere with the participant's ability to comply with study requirements or
--	--

	
that may impact the quality or interpretation of the data obtained from the study.
 
5. Are using tricyclic antidepressants or beta-adrenergic blocker drugs (both oral and topical).

Study Stopping Rules	
Study enrollment and treatment will be suspended pending expedited review of all pertinent data after the occurrence of:
 
1) One death if at least possibly related to the investigational agent2) Two Grade 4 systemic reactions (see Table 12.3.1.1c) possibly related to the injection of the immunotherapy agent3) Grade 4 local reaction (see Table 12.3.1.1a) or Grade 4 systemic reaction (see Table 12.3.1.1c) possibly related to the Nasal Allergen Challenge (NAC)
a. The study will be halted for this occurrence pending review of pertinent data by DAIT MM and the DSMB.

4. GENERAL ANALYSIS AND REPORTING CONVENTIONS

The following analyses and reporting conventions will be used:

- Categorical variables will be summarized using counts (n) and percentages (%) and will be presented in the form “n (%).” Percentages will be rounded to one decimal place. If a count is 0, 0% will be shown for the percentage.
- Continuous variables will be summarized using sample size (n), mean, standard deviation (SD), median, first and third quartiles, minimum (min), and maximum (max), as appropriate. The mean will be reported at one more significant digit than the precision of the data, the standard deviation will be reported at two more significant digits than the precision of the data, and first and third quartiles, minimum, maximum, and median will be reported at the same precision as the data. The median will be reported as the average of the two middle numbers if the dataset contains an even number of observations.
- Test statistics including t, z, and χ^2 test statistics will be reported to two decimal places.
- P-values will be reported to three decimal places if greater than or equal to 0.001. If less than 0.001, the value will be reported as “<0.001.” A p-value can be reported as “1.000” only if it is exactly 1.000 without rounding. A p-value can be reported as “0.000” only if it is exactly 0.000 without rounding.
- Each data listing will be sorted by treatment arm and subject identifier (ID) unless otherwise noted.

If departures from these general conventions are present in the specific evaluations section of this SAP, then those conventions will take precedence over these general conventions.

5. ANALYSIS SAMPLES

[ICH E3: 11.4.2.6](#); [ICH E9: 5.2](#)

The following groups of participants will define samples for endpoint analysis:

- **Modified Intent-to-treat (ITT) sample:** All participants who are randomized, received at least one dose of study treatment, and receive at least one dose during the 12-month NAC. Participants will be analyzed according to the treatment arm to which they were randomized, regardless of the medication they actually received.
- **Safety sample:** All participants who sign consent and undergo study procedures at Screening. Participants will be analyzed according to the medication they actually received, regardless of the treatment arm to which they were randomized. Non-treatment-emergent adverse events (e.g., any adverse event that occurs before the first injection) will be summarized in all participants who are enrolled, while treatment-emergent adverse events (e.g., any adverse event that occurs on or after the first injection) will be summarized in the safety sample.
- **Per-protocol (PP) sample:** All participants who are randomized, are escalated to at least 0.4 mL of the 1:10 maintenance dose, and receive at least 3 doses of maintenance SCIT/placebo.

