6. STUDY SUBJECTS

6.1. Disposition of Subjects

[ICH E3: 10.1](#)

The disposition of all enrolled subjects will be summarized in tables and listed. The following disposition information will be summarized:

- The number of participants screened.
- Among screened participants:
 - The number and percentage of participants who failed Screening, including those that attended the Screening visit but did not meet the inclusion/exclusion criteria.
 - The number and percentage of participants in the mITT sample.
 - The number and percentage of participants in the safety sample.
 - The number and percentage of participants in the PP sample.
- Among participants in the mITT sample and grouped by treatment arm:
 - The number and percentage of participants in the safety sample.
 - The number and percentage of participants in the PP sample.

National Institute of Allergy and Infectious Diseases
{Statistical Analysis Plan - Protocol #}

- The number and percentage of participants who completed the 12 month NAC.
- The number and percentage of participants who withdrew during the study due to:
 - Withdrawal by participant
 - Lost to follow-up
 - Death
 - Pregnancy
 - Physician decision
 - Participant experienced an anaphylactic reaction to study drug injection
 - Participant was diagnosed with an exclusionary malignancy
 - Participant acquired an opportunistic infection
 - Non-compliance with the study protocol
 - Participant refused protocol-mandated procedure at the Screening of Treatment Initiation Visit
 - Adverse Event
 - Other

A data listing of subject disposition will be provided for the mITT population.

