6.2. Demographic and Other Baseline Characteristics

ICH E3: 11.2

Summary descriptive statistics for demographic and baseline characteristics will be summarized in the mITT population grouped by randomized treatment arm and overall.

Demographic data will include age at randomization, sex, race, ethnicity, and site.

Baseline will be defined as the last measurement prior to or on the day of randomization (beginning of Month 0). Baseline characteristics will include:

- Age
- Sex
- Race
- Caretaker completed high school
- Annual household income (<15k)
- CASI & CASI subscales
- Cockroach-specific IgE and IgG4
- NAC Responsive Dose

National Institute of Allergy and Infectious Diseases
{Statistical Analysis Plan - Protocol #}

Demographic and baseline characteristics for continuous variables will be summarized using the number of participants, mean, standard deviation, median, and first and third quartiles (as applicable). Demographic and baseline characteristics for qualitative or categorical variables will be summarized by the number and percentage of participants within each category. Demographic and baseline characteristics in the mITT sample will also be compared between treatment arms using T-tests, Wilcoxon Sign-Rank Tests, or Chi-Square Tests, as applicable.

A data listing of demographics, baseline characteristics, and medical history will be provided for the mITT sample. A data listing of any inclusion/exclusion criteria not met will also be provided for all screened participants as well as all participants in the mITT sample separately.

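### SAP disposition, baseline and IgE/IgG4 displays are tied to an mITT sample that requires the 12-month NAC, and no disposition line counts participants randomised or treated by arm

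*SAP*

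**What the plan says.** **Samples (SAP 5).** The mITT sample is "All participants who are randomized, received at least one dose of study treatment, and receive at least one dose during the 12-month NAC". Protocol 13.4.1 has the same definition. The safety sample is "All participants who sign consent and undergo study procedures at Screening". The per-protocol (PP) sample requires randomisation, escalation to a stated dose, "and receive at least 3 doses of maintenance SCIT/placebo"; it has no NAC condition.

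**Disposition (SAP 6.1).** The section opens: "The disposition of all enrolled subjects will be summarized in tables and listed". It then gives counts among screened participants with no arm stated, followed by one block headed "Among participants in the mITT sample and grouped by treatment arm". After a page break come a line on completing the 12-month NAC and one beginning "The number and percentage of participants who withdrew during the study due to". The section closes: "A data listing of subject disposition will be provided for the mITT population".

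**Baseline (SAP 6.2).** "Summary descriptive statistics for demographic and baseline characteristics will be summarized in the mITT population grouped by randomized treatment arm and overall". The between-arm tests and the baseline listing are also in mITT.

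**Antibodies (SAP 8.3.4, 8.3.5 and 14.1).** Both the ANCOVA and the mixed-model sensitivity analysis of German cockroach-specific IgE and IgG4 are limited to mITT. Protocol 13.4.4.2 names no population for them.

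**Timing (protocol 8.8).** The 12-month NAC and blood draw both belong to the final visit.

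**The concern.** Membership of mITT depends on something that happens about a year after randomisation. That can be a workable choice for an endpoint measured by the NAC. It is a poor choice for disposition and baseline displays, whose purpose is to show who was randomised, who was lost, from which arm and why. A child who left before the final visit is outside mITT by definition, and so is missing from the displays that ought to describe the loss.

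At stake is the reader's ability to check whether children without a 12-month NAC differ between arms in number, reason or baseline. Some grounds for stopping therapy in protocol 11.2.1 concern reactions or failure to reach maintenance, so unequal loss is plausible, although the documents do not show it. The check is needed whether the primary analysis is complete-case (SAP 8.1.3) or multiply imputed (SAP 8.2 and 14.1), a conflict that the SAP leaves open, because an mITT analysis excludes these children under both.

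For IgE and IgG4 the restriction also selects participants on a procedure that serum does not require.

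**Working it through.** The plan gives no attrition rate and no expected mITT size, so there is no figure of its own to reproduce here. The check is a reading of the population rules.

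**1. What the two lines clearly inside the by-arm block can show.**
- Safety sample within mITT: every mITT member was randomised, and everyone randomised had consented and been screened. So mITT ⊂ randomised ⊂ safety sample, and the percentage is 100% in each arm by construction.
- PP within mITT: PP has no NAC condition, so PP is not a subset of mITT. The count shown is at most the full PP count and omits any PP child without a 12-month NAC.

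**2. The NAC-completion and withdrawal lines.** The available text does not show their level in the bullet list.
- If nested under mITT, NAC completion is reported only among children who had already begun that NAC, and withdrawals before it are not counted.
- If not nested, protocol 13.4.6, which asks for descriptive analyses by arm and includes study disposition, implies an arm split. The SAP still states no denominator.

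Neither reading states withdrawals by arm with all randomised participants as denominator.

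**3. Opening against closing sentence of SAP 6.1.** The opening covers everyone enrolled, and protocol 8.4.1 places enrolment at consent. The only disposition listing specified is for mITT. The two do not agree.

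**4. Baseline.** Table, tests and listing are all mITT. The listing of unmet eligibility criteria does cover all screened participants, but it does not show baseline characteristics by arm. The baseline of randomised children without a 12-month NAC is therefore not displayed.

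**5. Antibodies.** Protocol 8.2.1 ties the 12-month sample to time on treatment, not to the NAC. SAP 8.1.2 says the NAC stayed restricted when injection visits resumed after the COVID-19 suspension. A 12-month sample without a NAC is therefore possible, and that child would be dropped. Blood from an Early Termination Visit (protocol 8.9) is a different matter, because it need not be a 12-month sample.

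**6. What other displays supply.**

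| Display | What it gives | What is still missing |
|---|---|---|
| Screened and screen-failure counts (SAP 6.1) | A bound on the total | Any split by arm |
| Adverse events, including those leading to discontinuation (SAP 9.3) | Events by arm in the safety sample, by medication received | Randomised counts; reasons other than adverse events |
| Compliance (SAP 7.3) | Maintenance dosing by arm | Children who never reached maintenance |

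**7. Count.** Limited to mITT: by-arm block, disposition listing, baseline table, baseline tests and baseline listing = 5 displays. Adding the 2 antibody analyses gives 5 + 2 = 7. These reflect three population choices (disposition, baseline, antibodies), not seven separate faults.

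**The case against.** **The withdrawal table may be adequate.** The bullet level is lost in the available text, which is not a fault of the plan. One listed withdrawal reason refers to refusing a procedure at an early visit, which hardly fits children who reached the final NAC and so favours the wider reading. Protocol 13.4.6 would then supply the arm split; the SAP's primacy rule (SAP 2) applies only where the documents differ. This stands. A reader might infer that withdrawals by arm will not be reported at all, but the documents do not establish that. What remains is the unstated denominator.

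**Other SAP displays are by arm.** Correct: SAP 7.3 and 9.3 are. The statement about a single by-arm block holds only within SAP 6.1. The adverse-event denominators may suggest how many were treated, but they do not give numbers randomised.

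**Imputation may bring some children back.** SAP 8.2 names both mITT and PP. If PP is analysed separately with imputation, a PP child without a NAC could enter that analysis. This stands, but it does not help the mITT analysis or the displays discussed here.

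**The antibody point is hypothetical.** Blood and NAC share a visit, a NAC can be rescheduled (protocol 8.1.5), and out-of-window data are kept (SAP 8.1.2). mITT is also used for the other NAC endpoints, so the choice is consistent. All of this stands as a limit on size. It gives no reason to condition a serum endpoint on a nasal procedure.

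**Describing baseline in the analysed set is common.** True, and that table can stay. It cannot stand in for a table of those randomised.

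**Conclusion.** The point holds as a reporting and population problem and should be fixed. Followed as written, the SAP has no 6.1 line for numbers randomised or treated by arm, a disposition listing that contradicts its own lead-in, baseline displays that omit randomised children without a 12-month NAC, and antibody analyses limited by a procedure they do not need.

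The size in participants is unknown. No attrition figure can be derived, and the number with 12-month serum but no NAC may be zero. The conclusion rests on the population statements as written and does not depend on how the bullets after the page break are nested.

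Two stronger inferences should be resisted. A reader might conclude that the primary result is biased; the documents show no difference in loss between arms, and neither the primary estimate nor its test changes here. A reader might also conclude that the SAP departed from the protocol in defining mITT; the definition is the same in both, and the objection is only to where it is used.

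**What to change.** - **SAP 6.1:** add the numbers randomised and treated by arm. Report 12-month NAC completion and withdrawal reasons by arm, with all randomised participants as the stated denominator. Extend the disposition listing to all randomised participants and reconcile it with the opening sentence.
- **SAP 6.2:** give the baseline table by arm for all randomised participants, keeping the mITT table if wanted.
- **SAP 8.3.4, 8.3.5 and 14.1:** analyse IgE and IgG4 by randomised arm in all randomised and treated participants with a 12-month sample, with mITT as a sensitivity analysis.

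The cost is SAP wording and table denominators. Baseline and serum data are already collected, and protocol 11.3 already has withdrawal reasons recorded on the case report form. No new data and no change to the primary analysis are needed.

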12.4 Collection and Recording of Adverse Events

12.4.1 Collection Period

Adverse events (including SAEs) will be collected from the time of consent until 30 days after a participant completes study participation or until 30 days after he/she prematurely withdraws (without withdrawing consent) or is withdrawn from the study.

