13.4.4 Analyses of Secondary and Other Endpoints

13.4.4.1 Safety

Safety will be summarized by arm in the safety sample by the number and percentage of serious and non-serious adverse events stratified by grade and relationship to treatment as well as the number and percentage of participants who have a serious and non-serious adverse event stratified by grade and relationship to treatment.

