8.3. Secondary Endpoints

8.3.1. Endpoint 1

Variable: Number of immunotherapy related adverse events, overall and by participant, and number of immunotherapy related serious adverse events in the course of treatment.

Analysis: Summary tables will present the total number of events as well as the number and percentage of subjects experiencing the events. If a subject experiences the same AE on multiple occasions, the event will be counted once for each occurrence when reporting the number of AEs. When reporting the number of subjects experiencing the events, a subject will only be counted once if they experience an event within the particular system organ class or preferred term. Percentages will be based on the number of subjects in the safety population.

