9.3. Adverse Events

[ICH E3: 12.2](#)

All AEs will be classified by system organ class (SOC) and preferred term, according to a standardized thesaurus (Medical Dictionary for Regulatory Activities [MedDRA]). The latest edition of MedDRA will be used at the time of classification.

The severity of AEs will be classified, as applicable, using the criteria set forth in the NCI-CTCAE Version 4.03.

Each AE will be entered on the electronic case report form (eCRF) once at the highest severity.

The relationship, or attribution, of an AE to the study therapy regimen or study procedures is defined in Protocol Section 12.3.2.

National Institute of Allergy and Infectious Diseases
{Statistical Analysis Plan - Protocol #}

Overall summary tables will be developed using the Safety Population to report the number of events and the number and percentage of participants having at least one event in the following categories:

- AEs
- AEs by maximum grade
- AEs by relationship to a study drug

AEs classified by treatment arm, MedDRA SOC, and preferred term will be summarized in the Safety Population for each of the following categories:

- AEs
- AEs by maximum grade
- AEs by relationship to study drug

Summary tables will present the total number of events as well as the number and percentage of participants experiencing the events. If a participant experiences the same AE on multiple occasions, the event will be counted once for each occurrence when reporting the number of AEs. When reporting the number of participants experiencing the events, a participant will only be counted once if they experience an event within the particular SOC or preferred term. Percentages will be based on the number of participants in the safety population.

Similar summaries will be generated for SARs (defined in Protocol Section 12.2.1.1) and AEs leading to discontinuation of study drug separately.

Data listings will be provided separately for AEs, SARs, and AEs leading to discontinuation of study drug.

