	Secondary/MCP	
 Variable: Change in log-transformed German cockroach-specific IgE and IgG4 from baseline to 12 months. Analysis: For the mITT population, 12-month log-transformed IgE and IgG4 will be modeled as ANCOVA with factors for treatment arm, site, and the respective log-transformed baseline as covariates. Geometric least square means (LSmeans) and associated SEs will be presented for each treatment group. The geometric least square mean ratio comparing treatment vs placebo group, associated 95% confidence interval (CI) and p-value will be presented.
	Sensitivity	
 Analysis: For the mITT population, baseline and 12-month log transformed IgE and IgG4 will be modeled using a linear mixed model that will include a random intercept and fixed effects for each treatment arm, site, and an interaction term between treatment arm and time of measurement. Similarly to the ANCOVA, geometric least square means (LSmeans) and associated SEs will be presented for each treatment group. The geometric least square mean ratio comparing treatment vs placebo group, associated 95% confidence interval (CI) and p-value will be presented

Secondary Objective: To compare efficacy of cockroach subcutaneous immunotherapy (SCIT) superiority within placebo/active in participants with participants with asthma and german cockroach sensitization with respect to:
		
Safety Category 1 (e.g., AEs)		
 Variable: Rate of immunotherapy related adverse events and immunotherapy related serious adverse events in the course of treatment Analysis: For the safety samples, the difference in the number and percentage of serious and non-serious adverse events between treatment groups. The analysis will be stratified by grade.

National Institute of Allergy and Infectious Diseases
{Statistical Analysis Plan - Protocol #}

IES = Intercurrent event(s) strategy; PLS = Population-level summary; MCP=Multiple comparisons procedure

All estimand attributes explicitly identified for primary/secondary and select key estimands only.

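### The safety sample requires no injection, yet it is grouped by product received and supplies the denominator for treatment-emergent events, so never-injected children belong to it without an arm.

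*SAP*

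**What the plan says.** The safety sample is defined in the same terms in SAP 5 and Protocol 13.4.1: "All participants who sign consent and undergo study procedures at Screening". The bullet then says that these participants are analysed by the product they were actually given, and that "treatment-emergent adverse events (e.g., any adverse event that occurs on or after the first injection) will be summarized in the safety sample". Events before the first injection go to all enrolled participants.

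The neighbouring bullet, for the modified intent-to-treat sample, does require treatment: "All participants who are randomized, received at least one dose of study treatment, and receive at least one dose during the 12-month NAC".

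Four places rely on the safety sample:

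- SAP 8.3.1 (secondary endpoint 1, immunotherapy-related events): "Percentages will be based on the number of subjects in the safety population".
- SAP 9.3 (adverse event tables): "Percentages will be based on the number of participants in the safety population".
- SAP 14.1 (estimand table, safety row): "the difference in the number and percentage of serious and non-serious adverse events between treatment groups".
- Protocol 13.4.4.1: "Safety will be summarized by arm in the safety sample".

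**The concern.** The membership rule and the grouping rule do not cover the same children. Membership needs only consent and a screening procedure; grouping needs a product to have been given. Screen failures, and any child randomised but not injected, satisfy the first and cannot be placed by the second.

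Safety is the first secondary objective, and the first secondary endpoint is the rate of immunotherapy-related events. Children who never received an injection cannot have such an event. If they are counted in a denominator, the percentage is too low, and the size of the error depends on how many children failed screening, which has nothing to do with the safety of the extract.

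**Working it through.** The plan states no figure to reproduce. The check is a comparison of passages, followed by arithmetic on assumed counts.

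**1. Membership against grouping (SAP 5).**

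- Screen failure who had a screening procedure: in the sample; no product received; no arm.
- Randomised but not injected: in the sample; no product received; no arm.
- Injected: in the sample; arm given by the product received.

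The first group is expected to exist. Protocol 8.4.1 and 8.4.2 settle eligibility after consent, and SAP 6.1 plans to count children who attended Screening and failed. The second is at least foreseen, since the modified intent-to-treat definition lists randomisation and dosing as separate conditions.

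**2. Is there a narrower definition elsewhere?** SAP 9.1 refers to Section 4 for the safety sample, but Section 4 holds only reporting conventions. The pointer is a clerical slip and supplies no other definition. Protocol 13.4.1 matches SAP 5, and SAP 12 records a change only to the per-protocol sample.

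**3. Enrolled set against safety sample.** The bullet separates pre-injection events (enrolled participants) from treatment-emergent events (safety sample). Protocol 8.4.1 treats a child as enrolled once consent is signed. The two sets then differ only by children who consented but had no screening procedure, so the intended contrast nearly disappears. The distinction matters because "Adverse events (including SAEs) will be collected from the time of consent until 30 days after a participant completes study participation", so events can arise in children who are never injected.

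**4. Size for a pooled percentage.** Let T be the number injected, S the number consented and screened, and e the number of injected children with a treatment-emergent or immunotherapy-related event. Never-injected children add nothing to e.

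- Percentage among injected = e/T
- Percentage on the safety sample as written = e/S
- Ratio of the second to the first = T/S

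T = 80 is the accrual target (Protocol Synopsis and 3.1), taken as all injected. S and e are assumptions, because the documents give neither a screening yield nor an event rate. With e = 24, the figure among injected children is 24/80 = 30.0%. On the sample as written:

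- S = 100: 24/100 = 24.0%; ratio 80/100 = 0.80
- S = 120: 24/120 = 20.0%; ratio 80/120 = 0.67
- S = 160: 24/160 = 15.0%; ratio 80/160 = 0.50
- S = 320: 24/320 = 7.5%; ratio 80/320 = 0.25

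**5. By-arm percentages.** With 1:1 allocation and all 80 injected as assigned, each arm has 80/2 = 40 children. If columns are formed by product received, each arm's denominator is 40 and its percentage is the same as under a dosed definition. The columns add up to 80 while the safety N at S = 100 is 100, leaving 100 − 80 = 20 children in neither column.

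**The case against.** The strongest reply is that this is a drafting slip whose intent is plain. Setting enrolled participants against the safety sample makes sense only if the safety sample means treated children. A programmer grouping by product received would leave uninjected children out of both columns, and the safety outputs are mainly described by arm (Protocol 13.4.4.1, SAP 9.3, SAP 14.1). The overall summary tables in SAP 9.3 may simply be top-level tables not broken down by organ class, rather than tables pooled across arms. Most of this stands. It limits the consequence, but it does not repair the definition: the text never says that uninjected children are omitted, and the stated denominator is the size of the whole sample.

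A reader might infer two stronger things, and the documents support neither.

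- *That the comparison between arms is diluted.* Grouping by product received implies that never-injected children sit in neither arm, so arm percentages are very likely unaffected.
- *That the adverse event tables mix screening-procedure events with post-injection events, so that percentages could be biased in either direction.* SAP 9.3 labels its tables only as adverse events, which is loose. But SAP 5 already sends pre-injection events to the enrolled set and treatment-emergent events to the safety sample. Read together, the SAP 9.3 tables hold treatment-emergent events. What remains is a label to tighten.

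**Conclusion.** The definition is wrong as written and should be corrected, although the practical consequence is limited. Never-injected children belong to the safety sample, have no arm in it, and count in its size, which SAP 8.3.1 and 9.3 name as the denominator.

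The numerical effect is conditional. A pooled treatment-emergent or immunotherapy-related percentage taken on the full safety N is multiplied by injected/(consented and screened): 0.80 for 80 injected of an assumed 100 screened, and 0.25 at an assumed 320. That range illustrates the arithmetic and is not an estimate for this trial. The plan does not clearly commit to a pooled percentage. For the by-arm tables, the likely result is correct percentages with arm totals that fall short of the reported safety N. The stopping rules and the efficacy analyses do not use this sample.

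**What to change.** - In SAP 5, and in Protocol 13.4.1 for consistency, define the safety sample as all participants who received at least one injection of extract or placebo, analysed by the product received.
- Use it for SAP 8.3.1, SAP 9.3 and 9.4, and the safety row of SAP 14.1, and state that those tables hold events from the first injection onward.
- Keep pre-injection events in a separate set, as SAP 5 already plans, but name it as the consented and screened set, because enrolled means only that consent was signed.
- Record the change in SAP 12.

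The cost is wording only; no new data are needed. SAP 2 gives the SAP primacy over the protocol, so the SAP edits suffice for the analysis. Any pooled treatment-emergent or immunotherapy-related percentage would rise by S/T, for example 100/80 = 1.25 times at an assumed 100 screened. By-arm percentages do not change if uninjected children would have been left out of the arm columns anyway, and the arm totals will then add up to the safety N.
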